4.5 Continuing treatment

4.5.1 Continuing treatment for patients transferred from the JAGA Compassionate Use study

After consent to the investigator-initiated JAK inhibitor treatment in AGS study, transferred patients will undergo review of the patient's clinical condition, AEs, and blood tests for safety by the Principal Investigator. Safety laboratory assessments will be reviewed by the investigator along with a copy of the patient's diary, AEs and concomitant medications. If the patient is responding adequately to treatment (average diary score <0.5) or reduction in average diary score, the patient will continue receiving baricitinib therapy with follow-up appointments according to the Study Schedule (Appendices 1 and 2), based on the timelines of the most recent study visit on the JAGA Compassionate Use study (CHOP IRB Study #13205). If the patient is responding to treatment, but has not yet reached symptom control, dose escalation may be performed as discussed above and in Appendices 3 and 4. Once the patient has reached a stable dose of baricitinib, the same total dose may be administered as equal or unequal divided doses (administered up to 4 doses in a day [24 hours]).

4.5.2 Continuing treatment for patients originally consented to this study

After the patient has received baricitinib at the target dose level, the patient will have an evaluation performed, which will include an assessment of the patient's clinical condition, AEs, and blood tests for safety per the Study Schedule (Appendices 1 and 2). Safety laboratory assessments will be performed and reviewed by the investigator along with a copy of the patient's diary. AEs and concomitant medications will be assessed over the phone or in person by the study team. If the patient is responding adequately to treatment (average diary score <0.5) or reduction in average diary score, the patient will continue receiving baricitinib therapy with follow-up appointments according to the Study Schedule (Appendices 1 and 2). If the patient is responding to treatment, but has not yet reached symptom control, dose escalation may be performed as discussed

above and in Appendices 3 and 4. Once the patient has reached a stable dose of baricitinib, the same total dose may be administered as equal or unequal divided doses (administered up to 4 doses in a day [24 hours]).

This section also applies to patients who continue treatment beyond Week 288.

4.6 Immunosuppression monitoring during continuing treatment

Recent data has clarified that subjects with AGS are at risk of hematologic disturbances, including neutropenia⁶³. In addition, baricitinib is associated with neutropenia and leukopenia. However, AGS subjects treated with baricitinib typically have transient neutropenia and leukopenia that is not clinically significant⁶³. As part of ongoing safety monitoring, we will continue to assess every 3 months the following laboratory studies: T cell subsets, immunoglobulins and CBC with differential. If these tests are all normal (CD4 >250 cell/µl, ALC (Absolute lymphocyte count)>500/mm³, IgG >400mg/dL, ANC (Absolute Neutrophil Count) >1000/mm³), we will continue to follow immune function every 3 months.

If individuals have abnormalities on ANY of the proposed testing (CD4 <250 cell/ μ l, ALC <500/mm³, IgG <400mg/dL, OR ANC <1000/mm³), following management plans will be put in place and prophylaxis initiated (Appendix 10).

a. Patients will be followed as per Appendix 10 with repeat CBC and immune phenotyping and drug tapering or discontinuation considered as per Appendix 14. b. For persistent abnormalities, patients will be clinically referred to an immunologist for clinical care with their local care team and will be asked to continue to clinically follow with this expert for immunosuppression as defined by CD4 <250 cell/µl, ALC <500/mm³, IgG <400mg/dL, OR ANC <1000/mm³. c. Prophylactic approaches will also be put in place if patients on baricitinib have persistent abnormalities meeting specific criteria (Appendix 10).

4.7 Concomitant Medication

All concomitant medication taken during the study must be recorded on the eCRF.

After starting baricitinib, if the patient, for any reason, requires treatment with another therapeutic agent that has been demonstrated to be effective for treatment of the study indication, tapering from protocol therapy occurs at start of or before the new agent is started. This is considered an event in the statistical analysis. Exceptions to this rule: 1. Topical and inhaled corticosteroids are allowed.

2. Pulses of corticosteroids (prednisone, hydrocortisone, dexamethasone, or methylprednisolone) at any dose for less than 7 days (consecutive or cumulative) in a 28-day window are allowed.

3. Daily hydrocortisone for adrenal insufficiency is allowed.

4. Treatment for immune mediated hemolytic anemia or Immune mediated thrombocytopenia is allowed.

5. If a patient is enrolled and is taking immune suppression at the time of initiation of baricitinib and stops this other immune suppressant for any reason, that immune suppressant can be restarted.

Use of other concomitant medications will follow the parameters outlined in Appendix 16.

4.8 Dosing changes

On occasion, if drug related adverse events are seen, changes or discontinuation of study medication will be considered. Because abrupt drug discontinuation may result in rebound inflammation, tapering of dosing to the next dosing increment (e.g. 2 mg three times a day to 2 mg twice a day – Appendix 14) may be considered in response to suspected drug related adverse events. Repeat laboratory testing will be performed after drug tapering and results will be discussed with the study team to assess that drug continuation at a lowered dose is in the best interest of the patient.

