BID = twice daily, eGFR = estimated glomerular filtration rate, QID = 4 times daily, TID = 3 times daily.

a If there was a change in the patient's weight during the study, this would place the patient in a different weight range.

b Based on adult patient data as there is little data available in pediatric patients.

c. For the purposes of this protocol, we will define age based parameters for eGFR as follows: Normal renal function not requiring dose adjustments if: >12 months: At least a GFR of >60 ml/min/1.73 m2. <12 months: A GFR of >40 ml/min/1.73 m2. Patients will be excluded from enrollment if baseline eGFR was <30 ml/min/1.73 m2

The creatinine should be measured using the IDMS (Isotopic Dilution Mass Spectrometry) technique to monitor the eGFR if available. Other methods are allowed but are not preferred. Laboratory testing using other methods will not be used to monitor the eGFR.

The population PK analysis was updated including data from 71 juvenile and adolescent patients with Chronic Atypical Neutrophilic Dermatosis with Lipodystrophy and Elevated Temperature (CANDLE), CANDLE related disorders, STING-associated vasculopathy with onset in infancy (SAVI), and Aicardi-Goutières syndrome (AGS). The analysis has shown that while kidney function, as expressed by estimated GFR, is a statistically significant patient cofactor of the PK characteristics of baricitinib in this multi-disease patient population, the effects of eGFR on the kinetics of this patient population were not clinically relevant as they relate to dosing and did not support dose adjustment for patients with eGFR less than 120 mL/min/1.73 m².

Appendix 4. Dose Escalation Schedule for Patients with eGFR 30- <60 mL/min/1.73 m2 or for Age <24 Months with abnormal eGFR (see footnote below^c)

If a change in the patient's weight during the study would place the patient in a different weight range changes over time are permitted.

		Morning Dose	Noon Dose	Afternoon Dose	Evening Dose	Total Daily Dose	Dosing Frequency
eGFR 30 - < 60 mL/min/ *	1.73 m ^{2b}						I
10-< 20 kg	Initial	1 mg	1 mg	0 mg	1 mg	3 mg	TID
	Escalation 1	1 mg	1 mg	1 mg	1 mg	4 mg	QID
20-< 40 kg	Initial	2 mg	-	_	1 mg	3 mg	BID
	Escalation 1	2 mg	_	_	2 mg	4 mg	BID
≥ 40 kg	Initial	2 mg	_	_	2 mg	4 mg	BID
	Escalation 1	3 mg	-	_	3 mg	6 mg	BID

BID = twice daily, eGFR = estimated glomerular filtration rate, QID = 4 times daily, TID = 3 times daily.

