Appendix 13. Cutaneous LE Disease Area and Severity Index (CLASI)

Appendix 14. Dose tapering guidance

The following serves as guidance for dose tapering if necessary due to subject tolerance. If dose tapering is conducted for subject preference, dose tapering may occur more slowly, as needed for subject tolerance.

in two week increment unless resolution of AE requiring tapering * smaller dose increments obtained by pill cutter, until small pill size can be provided to patient where available

Initial dose	Dose decrease 1 #	Dose decrease 2 #	Dose decrease 3 #	Dose decrease 4 #	Dose decrease 5 #
1 mg bid	1 mg am and 0.5 mg* pm	0.5 mg* bid	0.5 mg am	stop	
1 mg tid	1 mg bid	1 mg am and 0.5 mg* pm	0.5 mg* bid	0.5 mg am	stop
1 mg qid	1 mg tid	1 mg bid	1 mg am and 0.5 mg* pm	0.5 mg* bid	stop
2 mg bid	1 mg tid	1 mg bid	1 mg am and 0.5 mg* pm	0.5 mg* bid	stop
2 mg tid	2 mg bid	1 mg * tid	1 mg * bid	0.5 mg* bid	stop
2 mg qid	2 mg tid	2 mg bid	1 mg * tid	1 mg* bid	stop
3 mg bid	2 mg bid	1 mg * tid	1 mg * bid	0.5 mg* bid	stop
3-2-3 mg	2 mg tid	2 mg bid	1 mg * tid	1 mg * bid	stop
3 mg qid	3-2-3-2 mg	2 mg qid	2-1-2-1 mg	1 mg qid	stop
4 mg bid	2 mg tid	2 mg bid	1 mg * tid	1 mg* bid	stop
4-2-4 mg	2 mg* qid	2 mg tid	2 mg bid	1 mg bid	stop
5 mg bid	4 mg bid	2 mg tid	2 mg bid	1 mg bid	stop
4 mg tid	2 mg* qid	2 mg tid	2 mg bid	1 mg bid	stop
6 mg bid	5 mg bid	4 mg bid	2 mg tid	2 mg bid	stop

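### Appendix 14, the table for toxicity dose reductions, omits one Appendix 4 starting dose, gives two taper sequences at 12 mg/day, and disagrees with the Appendix 11 and 12 worked example

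*Combined protocol and SAP*

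**What the plan says.** Section 4.8 allows a stepwise reduction for suspected drug-related adverse events, described as "tapering of dosing to the next dosing increment (e.g. 2 mg three times a day to 2 mg twice a day", with Appendix 14 as the reference. Section 4.9 and Appendices 10 and 12 also cite Appendix 14 for decreases. Appendix 11 uses the same notion of a next dose increment, and Section 9.4.2.2.3 links it to Appendix 14.

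Appendix 14 introduces itself thus: "The following serves as guidance for dose tapering if necessary due to subject tolerance". It has 14 rows, each keyed to a dosing pattern (amount and frequency) and not to a daily total. Three of them start at 12 mg/day. In each quote below, the starting pattern is followed by the first decrease: "6 mg bid 5 mg bid", "3 mg qid 3-2-3-2 mg" and "4 mg tid 2 mg* qid".

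Sections 4.5.1 and 4.5.2 say that, once the dose is stable, "the same total dose may be administered as equal or unequal divided doses", up to four times in 24 hours.

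Appendix 4 is titled "Dose Escalation Schedule for Patients with eGFR 30- <60 mL/min/1.73 m2 or for Age <24 Months with abnormal eGFR". Its initial dose for 20 to under 40 kg is 2 mg in the morning and 1 mg in the evening, 3 mg/day.

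In Appendix 11 (haemoglobin) and Appendix 12 (low platelets), two dose reductions are followed by taper to cessation if the abnormality recurs. Both illustrate the first reduction as 2 mg tid to 2 mg bid and the second as 2 mg bid to 1 mg bid.

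**The concern.** A reduction table keyed to dosing pattern works only if every pattern a patient can be on either has a row or has a rule that leads to one. A prescribed starting dose without a row leaves staff to improvise, and here that dose belongs to patients with reduced renal function. Where one daily total has two sequences, a permitted change in how the tablets are spread over the day changes what a single reduction means.

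The size of a step has consequences because the stopping rules in Appendices 11 and 12 are written as a number of reductions. Appendix 10 likewise moves to stopping if a very low neutrophil or lymphocyte count persists after one reduction. What counts as one reduction therefore decides the exposure at which a patient reaches cessation.

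**Working it through.** **Inputs.** Appendix 14 (14 rows), Appendix 3 (9 regimens), Appendix 4 (6 regimens), the worked examples in Section 4.8 and Appendices 11 and 12, and the re-division clause in Sections 4.5.1 and 4.5.2. Daily total = sum of the doses in a day (bid = 2, tid = 3, qid = 4 doses). Percentage cut = 1 − (total after ÷ total before).

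**Step 1: reproduce the protocol's own example.** Section 4.8: 2 mg tid = 6 mg/day, 2 mg bid = 4 mg/day; 1 − 4/6 = 33%. The Appendix 14 row for 2 mg tid gives the same first step.

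**Step 2: convert all 14 rows to mg/day.**

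| Start (mg/day) | Rows | Daily total at each step | First cut |
|---|---|---|---|
| 2 | 1 mg bid | 2, 1.5, 1, 0.5, stop | 25% |
| 3 | 1 mg tid | 3, 2, 1.5, 1, 0.5, stop | 33% |
| 4 | 1 mg qid; 2 mg bid | 4, 3, 2, 1.5, 1, stop | 25% |
| 6 | 2 mg tid; 3 mg bid | 6, 4, 3, 2, 1, stop | 33% |
| 8 | 2 mg qid; 3-2-3 mg; 4 mg bid | 8, 6, 4, 3, 2, stop | 25% |
| 10 | 4-2-4 mg; 5 mg bid | 10, 8, 6, 4, 2, stop | 20% |
| 12 | 6 mg bid; 3 mg qid | 12, 10, 8, 6, 4, stop | 17% |
| 12 | 4 mg tid | 12, 8, 6, 4, 2, stop | 33% |

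At 4, 6, 8 and 10 mg/day the listed rows agree at every step. At 12 mg/day they do not. After two reductions:
- 6 mg bid or 3 mg qid: 8 mg/day, cumulative cut 1 − 8/12 = 33%.
- 4 mg tid: 6 mg/day, cumulative cut 1 − 6/12 = 50%.

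The 12 mg/day total is the second escalation for patients of 40 kg or more in Appendix 3, prescribed there as 6 mg bid. Starting from that table, the other two patterns are reached by re-dividing it.

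**Step 3: match prescribed regimens to rows.** Of the 15 regimens in Appendices 3 and 4, 14 have a row. The exception is 2 mg + 1 mg in Appendix 4.

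**Step 4: count permitted re-divisions.** Assume whole-milligram doses (Section 1.4 limits tablets to 1 and 2 mg, unsplit), one to four doses a day, order ignored. Possible patterns against rows listed:
- 3 mg: 3 against 1
- 4 mg: 5 against 2
- 6 mg: 9 against 2
- 8 mg: 15 against 3
- 10 mg: 23 against 2
- 12 mg: 34 against 3

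In total, 3 + 5 + 9 + 15 + 23 + 34 = 89 patterns against 1 + 2 + 2 + 3 + 2 + 3 = 13 rows.

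**Step 5: compare the worked examples.** For a patient on 2 mg bid, the Appendix 11 and 12 example goes to 1 mg bid: 4 to 2 mg/day, a 50% cut. The Appendix 14 row goes to 1 mg tid: 4 to 3 mg/day, a 25% cut. Followed from 2 mg tid, two reductions end at 2 mg/day (1 − 2/6 = 67%) under the example and at 3 mg/day (1 − 3/6 = 50%) under Appendix 14.

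**The case against.** The case on the other side has real weight. Appendix 14 is labelled guidance, and Section 4.8 says only that tapering may be considered. Section 4.4.2 requires documented agreement among investigators and IRB approval for dose modifications, with an emergency exception, and Section 4.9 requires DSMB notification within 48 hours. A guidance table need not list every split. Among listed rows with a shared total only one is discordant, 4 mg tid, and it is not a prescribed regimen in Appendix 3 or 4. The missing row concerns one initial dose in one weight band and one eGFR stratum. In the preliminary safety table, no on-study eGFR abnormality among 35 patients exceeded grade 1, although the grade cut-offs are not stated.

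Most of this stands as a limit on the size of the problem, but it does not dispose of it. Appendix 10 tells staff to decrease the dose with reference to Appendix 14, and Appendices 11 and 12 say that patients should taper, so the triggers are firmer than Section 4.8 alone suggests. The missing dose is a prescribed one, not an unusual split.

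A reader might go further and infer that one trigger could produce no reduction, or a 17%, 33% or 50% cut. The documents do not support that as a single range. The 17% and 33% belong to 12 mg/day. For the unlisted 3 mg/day dose, 0% arises only by borrowing the 2 mg bid row (3 to 3 mg/day), and 50% only by borrowing the first decrease of the 1 mg bid row (3 to 1.5 mg/day). Both rows start from a different daily total; the same-total row, 1 mg tid, gives 33% (3 to 2 mg/day). Nor do the documents say that families choose the split or that re-division is unrestricted: it requires a stable dose and at most four doses a day.

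**Conclusion.** The point holds as a table inconsistency with a bearing on patient safety. It has three parts:
- one prescribed dose without a row;
- two sequences at 12 mg/day, differing by 2 mg/day after one reduction (10 or 8) and after two (8 or 6), with no stated handling for most other permitted splits;
- a conflict over the next step from 2 mg bid (2 or 3 mg/day).

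It would be tempting to add that reductions could not then be compared when tolerability is summarised. That does not follow from the plan: Section 6.3.5 summarises adverse events by type, body system, severity and relationship, and plans no analysis of reduction size. The power calculation is untouched. The documents do not say how many patients are on the doses concerned.

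The conclusion rests on reading bid, tid and qid literally. The count of unlisted splits also assumes whole-milligram doses. The missing row, the 12 mg/day discrepancy and the conflicting example do not depend on that second assumption.

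**What to change.** Reconcile Sections 4.5.1, 4.5.2 and 4.8, Appendix 4 and the worked examples in Appendices 11 and 12 with Appendix 14, so that:
- every dose in Appendices 3 and 4 has a row, including 2 mg + 1 mg;
- the protocol states how a re-divided dose is handled, and the 12 mg/day rows are either aligned or their difference is explained;
- the step from 2 mg bid is the same wherever it appears.

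The clinical team decides the steps and how the table is organised; no dose, step or indexing rule is proposed here. The cost is an edit to one table, alignment of the examples in two appendices, and a sentence in Section 4.5 or 4.8, made by protocol amendment. No statistical analysis changes.

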4.9 Subject Completion/Withdrawal

On occasion, the investigator may find it necessary to decrease (Appendix 14), temporarily interrupt or prematurely permanently discontinue investigational product administration following the occurrence of an AE or an abnormal laboratory finding. The investigator must notify the DSMB within 48 hours when decreasing, temporarily interrupting or prematurely permanently discontinuing therapy for an individual. If infection is the cause of the interruption, patients will receive treatment as clinically indicated for infections regardless of treatment decisions for baricitinib.

Any patient who is permanently discontinued from investigational product for an abnormal laboratory result should have the abnormal laboratory result reported as an AE, or an SAE if the laboratory abnormality results in an outcome requiring the AE to be reported as an SAE.

In addition, patients may be discontinued from the investigational product or from the study in the following circumstances:

- The patient enrolls in any other clinical trial involving an investigational product or in any other type of medical research judged not to be scientifically or medically compatible with this study.
- An SAE or a clinically significant change in a laboratory value occurs that, in the opinion of the investigator, merits the investigational product being discontinued and appropriate measures being taken.
- The investigator decides that the patient should be withdrawn from the study.
- The parents, legal guardian, or patient requests to be withdrawn from the study.
- Investigational product is no longer supplied.

4.9.1 Early Termination Study Visit

Subjects who withdraw from the study will have all procedures enumerated for the early termination visit as per the study schedule and timeline (Appendices 1 and 2) either in person or by telephone visit.

5 STUDY EVALUATIONS AND MEASUREMENTS

5.1 Screening and Monitoring Evaluations: Performed as Part of Clinical Care

5.1.1 Physical Examination

One complete physical examination (excluding pelvic and rectal examinations) will be performed at screening. This examination will determine whether the patient meets the criteria required to participate in the study and will also serve as a monitor for preexisting conditions and as a baseline for TEAE assessment. Body weight and height will also be recorded. Additional limited physical examinations will also be performed during the study (Study Schedule in Appendices 1 and 2). Fundoscopy may be completed as part of the physical exam if complaints of headache are present or irritability worsens on medication, and ophthalmology may be consulted as clinically indicated.

5.1.2 Vital Signs

Vital signs (blood pressure and pulse) will be measured at times indicated in the Study Schedule (Appendices 1 and 2). Any clinically significant findings that result in a diagnosis should be captured on the eCRF and reported as an AE. Additional measurements of vital signs may be performed at the discretion of the investigator.

5.1.3 Cardiac monitoring

Pulmonary hypertension (PH) is a rare but potentially fatal disorder characterized by severe vasculopathy and elevated pulmonary artery pressures leading to right-sided heart failure. Progressive PH has both genetic and inflammatory influences ²⁸⁻³⁴. In particular, type I interferons, as are overexpressed in AGS, have been established as risk factors for the development of PH ^{29,35-38}. We have identified several individuals within our cohort with PH, as related to systemic interferon overexpression (paper submitted). Cardiac involvement will be quantified using clinical assessment and echocardiogram. As per World Health Organization (WHO) guidelines, PH will be defined as persistently elevated mean pulmonary arterial pressure of ≥25 mmHg and a pulmonary capillary wedge pressure of \leq 15 mmHg for precapillary PH ⁶⁴. In setting of contraindication to cardiac catheterization (e.g. critical illness), combined echocardiographic and clinical evidence of PH will be utilized ⁶⁵. Individuals affected by AGS will have screening cardiac evaluations every other year, unless abnormalities are noted, on a clinical basis, with additional management as clinically indicated. If not previously performed on a clinical basis, this may be performed on a research basis. In the patients identified as being affected by PH, we will follow the relationship between PH, and the response to baricitinib.

5.1.4 Electrocardiograms

Twelve-lead ECGs will be obtained clinically during the screening process. A single 12lead ECG measurement will be performed at screening. Subsequently, ECGs will be obtained every other year as a part of clinical care to screen for pulmonary hypertension, in addition to echocardiograms every other year as discussed above. If not previously performed on a clinical basis, this may be performed on a research basis.

5.1.5 Chest X-ray and tuberculosis screening

During the screening process, we will review clinically obtained posterior-anterior view chest x-ray obtained within 6 months prior to the study. The chest x-ray will be reviewed by the investigator or his/her designee to exclude patients with active TB infection. In addition, patients will be tested at screening for evidence of active or latent TB as described above.

5.1.6 Laboratory Evaluations

Appendix 2 lists the schedule for sample collections in this study. Appendix 8 lists the specific tests that will be performed for this study. Some testing may occur outside of inperson study visits at CHOP and these will be considered as being performed as part of clinical care.

In order to address constraints on blood volumes for laboratory tests in younger patients (<1 year), alternative methods of assessing baseline risk of hepatitis, HIV, or TB (e.g. testing of parent) may be considered, as well as limited PK studies. These will be considered as being performed as part of clinical care.

